4.1 Definition of Disease Phases in Chronic Myeloid Leukemia

Chronic Phase

- 1. No significant symptoms, which are not readily controlled by conventional doses of hydroxyurea or busulfan.
- 2. None of the features of accelerated phase or blastic phase. (Note: Granulocytic hyperplasia and the Philadelphia chromosome may be present in the bone marrow).

Accelerated Phase (any one or more of the following criteria)

- 1. White blood count (WBC) difficult to control with conventional use of busulfan/hydroxyurea in terms of doses required or shortening of intervals between courses.
- 2. Rapid doubling of WBC (\leq 5 days).
- 3. \geq 10% blasts in blood or marrow.
- 4. \geq 20% blasts plus promyelocytes in blood or marrow.
- 5. \geq 20% basophils plus eosinophils in blood.
- 6. Anemia or thrombocytopenia unresponsive to busulfan/hydroxyurea.
- 7. Persistent thrombocytosis (≥ 1,000,000/ 1) unresponsive to conventional doses of hydroxyurea or busulfan.
- 8. Additional chromosome changes (evolving new clone).
- 9. Increasing splenomegaly unresponsive to conventional doses of hydroxyurea or busulfan.

- 10. Development of chloromas or myelofibrosis.
- 11. Patients in a second (or subsequent) chronic phase after blast crisis.

Blastic Phase/Blast Crisis

1. \geq 30% blasts plus promyelocytes in the blood or bone marrow.

5.0 ELIGIBILITY CRITERIA

- 5.1 Inclusion Criteria
 - 5.1.1 Patients with the following diagnoses are eligible for this study:
 - advanced myeloid malignancies with a disease status of >2nd remission, induction failure, or relapse
 - chronic myeloid leukemia in blast crisis
 - myelodysplasia, subtype: refractory anemia with excess blasts (RAEB)
 - 5.1.2 All candidates for this study must have a HLA (A, B, C, DR) identical sibling who is willing to donate bone marrow or primed blood stem cells or a 10/10 allele matched unrelated donor or minor mismatches as per BMT SOP that allows Tacrolimus and Sirolimus to be given for GVH prophylaxis. All ABO blood group combinations of the donor/recipient are acceptable since even major ABO compatibilities can be dealt with by various techniques. (Red cell exchange or plasma exchange).
 - 5.1.3 Prior therapy with VP-16, busulfan, hydrea and gleevec are allowed.
 - 5.1.4 Patients must be older than 6 years and the upper age limit for this study is 55 years.
 - 5.1.5 A cardiac evaluation with electrocardiogram and MUGA or echocardiogram is required for all patients. Patients must have an ejection fracture of greater than or equal to 50%.
 - 5.1.6 Patients must have a serum creatinine of less than or equal to 1.2 or creatinine clearance > 80ml/min.
 - 5.1.7 A bilirubin of less than or equal to 1.5. Patients should also have an SGOT and SGPT less than 5 times the upper limit of normal.
 - 5.1.8 Pulmonary function tests including DLCO will be performed. FEV $_1$ and DLCO should be greater than 50% of predicted normal value.
 - 5.1.9 Time from the end of last induction or reinduction attempt should be greater than or equal to 21 days.
 - 5.1.10 A signed (IRB approved) informed consent document is required. The patient, donor family member, and transplant team (physician, nurse, and social worker) meet together at least once prior to starting the transplant procedure to review all

pertinent risk/benefit information as part of the consenting process. Alternative treatment modalities are also discussed at this meeting.

- 5.2 Exclusion Criteria
 - 5.2.1 Prior radiation therapy/exposure that prevents the patient from receiving IMRT. (Determination will be made by the Radiation Oncologist.)
 - 5.2.2 Patients who have previously undergone a blood/marrow transplant and now have relapsed disease.
 - 5.2.3 Patients with a psychological or medical condition that the treating physician deems unacceptable to proceed to allogeneic bone marrow transplant.
 - 5.2.4 Pregnancy
 - 5.2.5 EKG showing ischemic changes or abnormal rhythm and echocardiogram showing ejection fraction <50% or abnormal wall motion.
- 5.3 Donor Inclusion/Exclusion Criteria
 - 5.3.1 Any sibling donor who is histocompatible with the prospective recipient will be considered a suitable donor.
 - 5.3.2 Donors will be excluded if for psychological or medical reasons they are unable to tolerate the procedure.
 - 5.3.3 Donor should be able to donate peripheral blood stem cells or bone marrow.

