6.0 TREATMENT PLAN

All patients will have a right atrial catheter, hickman type inserted. This catheter will be used for collection of blood specimens, administration of drug, bone marrow, blood components, and for hyperalimentation.

- 6.1 Pre-transplant evaluation will be performed within four weeks of beginning treatment except for the following: 1) Bone marrow aspirate and biopsy + cytogenetics within 14 days of starting treatment, 2). Complete blood count (CBC), differential, platelets, comprehensive metabolic panel within 5 days of starting treatment.
 - a. Prior to admission patient will have a complete history and physical examination performed. Special attention will be given to prior chemotherapy, height, weight and body surface area should also be noted.
 - b. Patients will have the following laboratory tests performed:
 - i. CBC with diff platelets
 - ii. Sodium, potassium, chloride, bicarbonate or total carbon dioxide, BUN, creatinine, Ca, Mg, Phosphorous, total bilirubin, total protein, albumin, SGPT, SGOT, LDH, alkaline phosphatase, glucose.
 - iii. Urine analysis HIV test

Hepatitis A, B + C 24-hr urine for creatinine clearance CMV, HSV – HZV ab Immunoglobulin levels

- iv. 24-hour urine collection for creatinine clearance.
- v. Chest x-ray and electrocardiogram (EKG)
- vi. CT scan of chest, abdomen and pelvis.
- vii. Pregnancy test
- c. Initial coagulation studies prothrombin time, APTT.
- d. MUGA scan or echocardiogram
- e. Pulmonary function tests, including DLCO
- f. A bone marrow aspirate and biopsy, and cytogenetics needs to be done within 2 weeks of admission (if bone marrow not aspirable and > 20% blasts in blood this may be done on peripheral blood sample).

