7.0 STUDY DESIGN AND RULES FOR DOSE ESCALATION

This is a single center phase I/II trial that consists of dose escalation (phase I portion), followed by expanded enrollment at the MTD (phase II portion). Registration and assignment to the dose level will be done at City of Hope (see section 11.0). The rules for dose escalation, dose expansion and termination of escalation are given in sections 7.1 and 7.2. Study design considerations and targeted response rates for the phase II portion of the trial are given in sections 10.2-10.4.

The goal of the phase I study is to evaluate the toxicity results for the combination of intensity modulated radiation therapy (IMRT) with IV busulfan [targeted to AUC (area under curve) of 700-900] and VP-16 as a preparative regimen for hematopoietic stem cell transplantation from an HLA-identical sibling or HLA-fully-matched unrelated donor. For the phase I portion of the study, the assessment will be done in two strata:

- Stratum 1: Adult patients (≥18 years, ≤55 years) with advanced myeloid malignancies or high-risk myelodysplasia.
- Stratum 2: Pediatric patients (6-17 years) with advanced myeloid malignancies or high-risk myelodysplasia.

The primary endpoint for the phase I portion of the study is the determination of the MTD in five doses to be tested in each of the above stratum.

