APPENDIX VIII

ELIGIBILITY CHECKLIST

	lusion C		wing criteria must all be marked VES
			wing criteria must all be marked YES.
1	Yes	No	Does the patients have documented acute myeloid leukemia not in first remission or second remission i.e. after failing remission induction therapy or in relapse or beyond second remission? OR Does the patients have chronic myeloid leukemia in blastic phase of the disease? NOTE: Patients with refractory anemia with excess blasts and in transformation will be aligible
			in transformation will be eligible.
2	Yes	No	Does the subject have a HLA (A, B, C, DR) identical sibling or fully-matched unrelated donor who is willing to donate bone marrow or primed blood stem cells?
			NOTE: All ABO blood group combinations of the donor/recipient are acceptable since even major ABO compatibilities can be dealt with by various techniques. (Red cell exchange or plasma exchange).
3	Yes	No	Has the patient had prior therapy?
			NOTE: Prior therapy with VP-16 and busulfan is allowed.
4	Yes	No	Patient must have reached their 6 th birthday and must not have passed their 55 th birthday.
			Age
5	Yes	No	Does the subject have an ejection fracture of greater than or equal to 50% by MUGA or echocardiogram? (Either method for measuring cardiac function is acceptable, however, the same scan must be used throughout treatment and follow-up to monitor the patient for cardiac toxicity.)
			Ejection fracture Date Obtained
6	Yes	No	Has the subject had an electrocardiogram?
			Date Obtained
7	Yes	No	Does the patients have a serum creatinine of less than or equal to 1.2 or creatinine clearance > 80ml/min?
			Serum Creatinine IULN
			Date obtained
3			Page 39 of 44 06/29/11

		Creatinine Clearance (estimated or measured – circle one)
		Date obtained
8Y	es No	Does the patient have a bilirubin of less than or equal to 1.5?
		Bilirubin
		Date obtained
9		Does the patient have a SGOT and SGPT less than 5 times the upper limit of normal.
		SGOTULN
		Date obtained
		SGPTULN
		Date obtained
10Y	esNo	Does the patient have FEV ₁ and DLCO greater than 50% of predicted normal value based on Pulmonary function tests?
		FEV1 Predicted Normal Value
		DLCO Predicted Normal Value
		Date obtained
11Y	es No	Is the time from the end of last induction or reinduction attempt greater than or equal to 21 days?
		End Date of treatment
12Y	es No	Has the patient signed the informed consent form approved by the IRB?
		Date informed consent form signed

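### The renal entry rule is an unscaled creatinine-or-clearance limit applied unchanged from age 6, so small children with clearly reduced renal function meet it.

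*Combined protocol and SAP*

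**What the plan says.** Section 5.1.6 reads: "Patients must have a serum creatinine of less than or equal to 1.2 or creatinine clearance > 80ml/min". Item 7 of the eligibility checklist (Appendix VIII) repeats it: "Does the patients have a serum creatinine of less than or equal to 1.2 or creatinine clearance > 80ml/min". The checklist field for the second limb begins "Creatinine Clearance (estimated or measured", so an estimated value is accepted as well as a measured one.

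Section 5.1.4 applies the same inclusion criteria from age 6 to age 55, and Section 7.0 defines a separate pediatric group: "Stratum 2: Pediatric patients (6-17 years) with advanced myeloid malignancies or high-risk myelodysplasia". The pediatric provisions in Sections 7.0, 7.2 and 10.2 concern dose escalation and enrolment. None changes an organ-function limit.

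Two neighbouring provisions matter. Lung function in 5.1.8 is set relative to the patient: "DLCO should be greater than 50% of predicted normal value". The pre-transplant work-up in 6.1 includes a "24-hour urine collection for creatinine clearance" and says that "height, weight and body surface area should also be noted".

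**The concern.** The two limbs are joined by 'or', and both are absolute numbers. Creatinine production rises with body and muscle size, so one serum value means different renal function in a 6-year-old and in an adult. For a mid-sized adult the limbs roughly agree. For a small child they separate:

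- The clearance limb, read literally, is out of reach even with normal kidneys.
- Entry therefore rests on creatinine of 1.2 or less, a lenient limit at that size.

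Reading the clearance limb as per 1.73 m² does not help, nor does using an estimated clearance. A child who fails that limb still enters on creatinine.

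At stake is entry safety in stratum 2. Children with reduced renal function could receive busulfan, VP-16 and escalating marrow irradiation without any written renal criterion stopping them.

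**Working it through.** The plan states no figure on this point, so there is none to reproduce. The check asks what function creatinine 1.2 implies at different body sizes.

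**Inputs from the plan:** creatinine limit 1.2 (no unit given), clearance limit 80 ml/min, pediatric ages 6-17.

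**Assumed inputs, not in the documents:** creatinine in mg/dL; estimated clearance per 1.73 m² = k × height (cm) / creatinine, with k from 0.413 to 0.55; smallest children 108-128 cm with body surface area 0.71-0.92 m²; normal clearance 100-120 ml/min/1.73 m².

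**Step 1. Function implied by creatinine 1.2 (ml/min/1.73 m²).**

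| Height | Low (k = 0.413) | High (k = 0.55) | As % of 80 |
|---|---|---|---|
| 108-128 cm | 0.413 × 108 / 1.2 = 37.2 | 0.55 × 128 / 1.2 = 58.7 | 46-73% |
| 140 cm | 0.413 × 140 / 1.2 = 48.2 | 0.55 × 140 / 1.2 = 64.2 | 60-80% |
| 172 cm | 0.413 × 172 / 1.2 = 59.2 | 0.55 × 172 / 1.2 = 78.8 | 74-99% |

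Against the assumed normal range, the smallest children are at 37.2 / 120 = 31% to 58.7 / 100 = 59%.

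**Step 2. Cross-check by creatinine mass balance.** Clearance = daily production / (serum creatinine × 1440 min), with assumed production of 15-20 mg/kg/day and creatinine of 1.2 mg/dL = 0.012 mg/ml. Surface area is √(height × weight / 3600).

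- 115 cm, 20 kg (0.80 m²): 15 × 20 / (0.012 × 1440) = 17.4 and 20 × 20 / 17.28 = 23.1 ml/min, or about 38-50 per 1.73 m².
- 128 cm, 26 kg (0.96 m²): 22.6-30.1 ml/min, or about 41-54 per 1.73 m².

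Both methods stay below 60 at these sizes.

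**Step 3. The clearance limb read literally.** To exceed 80 ml/min unscaled, the smallest children would need 80 × 1.73 / 0.92 = 150 to 80 × 1.73 / 0.71 = 195 ml/min/1.73 m². Normal function gives 80 ml/min only from a surface area of 80 × 1.73 / 120 = 1.15 m² to 80 × 1.73 / 100 = 1.38 m². This limb is too strict for small children, but because of the 'or' it excludes no healthy child. Its effect is to leave creatinine as the only working limb.

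**Step 4. Creatinine equivalent to 80 ml/min/1.73 m²** (k × height / 80):

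- 115 cm: 0.59-0.79
- 140 cm: 0.72-0.96
- 172 cm: 0.89-1.18

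**Step 5. Adult comparison.** With the assumed adult formula (140 − age) × weight / (72 × creatinine), a 40-year-old of 70 kg at creatinine 1.2 has 100 × 70 / 86.4 = 81 ml/min. The limbs agree there. Over ages 18-55 and weights 60-80 kg the result runs from 59 to 113 ml/min.

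**The case against.** The strongest reply is that the rule is lenient for everyone and that children are not singled out. Nobody is required to have 80 ml/min/1.73 m². By the same adult formula with a 0.85 factor for women, a 55-year-old woman of 50 kg at creatinine 1.2 has 85 × 50 × 0.85 / 86.4 = about 42 ml/min. At an assumed 157 cm (about 1.48 m²) that is about 49 per 1.73 m², inside the range found for the smallest children. This stands as far as it goes: some small, older adults also pass with low clearance. But in adults the result varies widely around 80. At 108-128 cm every estimate is below 60.

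A second reply is that the plan limits the harm. Busulfan is adjusted to measured exposure, the kidneys are spared in radiation planning, the protocol lists no nephrotoxicity for VP-16, and each pediatric dose level waits for adult experience. These features reduce the likely consequence. They do not make the entry rule screen renal function.

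A third is that the physician sees the 24-hour clearance, and the checklist appears to record a creatinine upper limit of normal. Neither enters the criterion. The remaining barrier is 5.2.3, which excludes "Patients with a psychological or medical condition that the treating physician deems unacceptable to proceed to allogeneic bone marrow transplant". It sets no renal threshold.

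Two further points are fair. Bilirubin and ejection fraction are also flat limits, so the contrast with the lung criterion is only supporting. The choice of k alone moves the estimates by about a third.

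**Conclusion.** The concern holds. That the rule is unscaled, joined by 'or' and unchanged from age 6 is plain from 5.1.6 and checklist item 7. That creatinine 1.2 means clearly reduced function in the smallest children depends on the assumed unit, heights and estimating constants, but the direction is the same throughout the ranges tried. The gap shrinks with size and nearly closes at the upper estimate for late adolescence.

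The point is confined to entry safety in stratum 2. The number of candidates in the gap cannot be estimated from the documents, and physician judgement may stop some of them. The change is worth making because it is cheap, not because harm has been shown.

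**What to change.** For patients under 18 only, in 5.1.6 and checklist item 7:

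1. State the clearance limb as above 80 ml/min/1.73 m², using the 24-hour clearance and body surface area already collected under 6.1.
2. Replace the flat 1.2 with age- or size-referenced creatinine limits consistent with that clearance, for example about 0.6-0.8 mg/dL at 115 cm. Final values are for the sponsor's clinicians.

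Both parts are needed, since scaling the clearance limb alone leaves the creatinine route open. The adult rule stays as written.

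The cost is a wording change in one criterion and one checklist line, with no new test. A few children may be refused. If children have already been enrolled, which the documents do not say, stratum 2 would contain two renal entry definitions. Its phase II part is exploratory, with at most nine additional children (Section 10.2), and the adult phase II analysis is unaffected.

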6.0 TREATMENT PLAN

All patients will have a right atrial catheter, hickman type inserted. This catheter will be used for collection of blood specimens, administration of drug, bone marrow, blood components, and for hyperalimentation.

- 6.1 Pre-transplant evaluation will be performed within four weeks of beginning treatment except for the following: 1) Bone marrow aspirate and biopsy + cytogenetics within 14 days of starting treatment, 2). Complete blood count (CBC), differential, platelets, comprehensive metabolic panel within 5 days of starting treatment.
 - a. Prior to admission patient will have a complete history and physical examination performed. Special attention will be given to prior chemotherapy, height, weight and body surface area should also be noted.
 - b. Patients will have the following laboratory tests performed:
 - i. CBC with diff platelets
 - ii. Sodium, potassium, chloride, bicarbonate or total carbon dioxide, BUN, creatinine, Ca, Mg, Phosphorous, total bilirubin, total protein, albumin, SGPT, SGOT, LDH, alkaline phosphatase, glucose.
 - iii. Urine analysis HIV test

Hepatitis A, B + C 24-hr urine for creatinine clearance CMV, HSV – HZV ab Immunoglobulin levels

- iv. 24-hour urine collection for creatinine clearance.
- v. Chest x-ray and electrocardiogram (EKG)
- vi. CT scan of chest, abdomen and pelvis.
- vii. Pregnancy test
- c. Initial coagulation studies prothrombin time, APTT.
- d. MUGA scan or echocardiogram
- e. Pulmonary function tests, including DLCO
- f. A bone marrow aspirate and biopsy, and cytogenetics needs to be done within 2 weeks of admission (if bone marrow not aspirable and > 20% blasts in blood this may be done on peripheral blood sample).
- g. Patients with acute leukemia or chronic myeloid leukemia in blast crisis will have a lumbar puncture performed. Methotrexate (10mg/m² but not more than a total dose of 12mg) will be administered intrathecally. The spinal fluid will be examined for the presence of malignant cells. Those patients who had leukemic central nervous system (CNS) involvement prior to the time of admission before transplantation will receive five weekly intrathecal methotrexate injections with the dose described above from the time patients platelet count is greater than 75,000 to day 100, then monthly intrathecal methotrexate injections with the dose described above between day 100 and 12 months after transplantation. The initial spinal tap will only be performed if patient's platelet count can be kept above 75,000.

6.2 Preparative Chemotherapy Regimen

(Note: Patient to sign consent form before starting Dilantin.)

[figure not shown]
Thursday/Day -19

Monday/Day -15

[figure not shown]
Begin dilantin 300mg/p.o. t.i.d. times 1 day, then 300mg/p.o./IV daily times 14 days.

Admission or outpatient, dilantin blood levels will be checked and dose adjusted as needed to meet therapeutic range. Further adjustments if clinically indicated. Busulfan test dose administered at 6:00 to 8:00 a.m. as a single dose. The IV dose is calculated as follows:

1. Body surface area (BSA) is calculated by the equation:

2. 22mg/m² IV Busulfan will be given over 2 hours. Blood levels will be obtained with the first dose as per appendix 1 and will be performed per current Hematopoietic Cell Transplant Program Clinical Manual of Standard Operating Procedures. Tuesday/Day -14 Busulfan AUC will be calculated per current Hematopoietic Cell Transplant Program Clinical Manual of Standard Operating Procedures. The resulting AUC will be used to determine the dose required to achieve an AUC of 800 µM* min according to the following formula:

The maximum dose given will not exceed $32mg/m^2$. There is no limit on dose reduction Busulfan dose will only be adjusted for AUC's <700 or >900 μ M*min.

- Wednesday/Day -13 The adjusted dose Busulfan dose will be given at 6 a.m. and blood levels will be repeated. Further dose adjustments will be performed if AUC >1000.
- Thursday/Day -12 Patient admitted to Bone Marrow Transplant (BMT) unit or receive further dose of Busulfan in clinic.

Busulfan dosing restarted at 12-noon if only one test dose of busulfan administered and at 6 p.m. if two doses administered. The adjusted dose is repeated every 6 hours for a total of 16 doses (including the test doses).

- Monday/Day -8 See Section 6.5 for treatment planning and delivery of total marrow and lymphoid irradiation.
- Saturday/Day -3 VP-16 30mg/kg based on adjusted ideal body weight will be administered.
- Tuesday/Day 0 PSC reinfusion/or BM infusion

PSC Collection as per current Hematopoietic Cell Transplant Program Clinical Manual of Standard Operating Procedures.

Toxicities of the marrow infusion are very rare. Volume overload may be prevented by removal of plasma from the marrow aspirate or by phlebotomy of the recipient prior to marrow infusion. Pulmonary emboli are theoretically possible and would require management with 02 or IPPB. However, our clinical observations over the last 20 years indicate that pulmonary embolism in this clinical setting does not occur at any increased rate. The most frequently encountered problem is that of chills, hives, and fever. Those allergic reactions occur rarely (in 1 to 2%) and can be prevented by intravenous injections of dyphenhydrimine 25mg and hydrocortisone (50mg) prior to the bone marrow infusion.

- 6.3 Graft Versus Host Disease (GVHD) Prophylaxis and Treatment
 - 6.31 GVH prophylaxis regimen will consist of the best available regimen excluding methotrexate.

- 6.32 If moderate to severe graft-versus-host disease occurs (Grade II-IV), patients will be treated with the administration of higher doses of methyl-prednisolone, anti-thymocyte globulin, etc.
- 6.33 Graft-versus-host disease will be graded according to previously defined criteria (Appendix III, IV).
- 6.4 Supportive Care will be given as per current Hematopoietic Cell Transplant Program Clinical Manual of Standard Operating Procedures.
- 6.5 Treatment Planning and Delivery of Total Marrow and Lymphoid Irradiation (TMLI).
 - 6.5.1. TMLI will be delivered using Helical Tomotherapy. Tomotherapy is an imageguided IMRT delivery device and is the only device currently capable of delivering the proposed TMLI radiation therapy. Therefore, for this trial all patients will be treated using the Tomotherapy system. In addition, all treatment planning will take place on the Tomotherapy HiArt treatment planning system.
 - 6.5.2. Simulation. All patients will undergo CT simulation with scanning from the top of the scalp to the level of the distal femurs. Prior to simulation, the patients will be fitted for an immobilization cast they will be treated in. Aquaplast facemask will be utilized for head positioning. A full-body immobilization cast will also be used (Vaclok). CT scans will be acquired at full inspiration, full expiration, and mid-inspiration.
 - 6.5.3. Treatment Planning. Treatment planning will take place on the Tomotherapy HiArt treatment planning system. The following organs will be contoured: lungs, heart, small and large intestine, kidneys, orbits, lenses, oral cavity, bladder, parotid glands, stomach, ovaries (if clipped for localization), testes, liver, spleen, esophagus, bone, and major lymph node chains. The target regions will include the bone, major lymph node chains, liver, spleen, testes, and brain. All other contoured organs will be treated as avoidance structures. Contouring for lungs, spleen, and kidneys will take into account organ position as full inspiration, full expiration, and mid-inspiration. The bone compartment will be contoured such that the entire ribcage bilaterally will be contoured as a separate region of interest. The skull will also be contoured as a separate region of interest. The gross tumor volume (GTV) will be the planning tumor volume (PTV). It is recommended that the treatment planning use a 25 mm slice thickness and a pitch of a least 0.35. A minimum of 80% of the targeted region is to receive the prescribed dose with a primary objective being to reduce the median dose (D₅₀) and maximum dose of which 90% of the organ receives (D_{90}) to a minimum. The table below provides guidelines for treatment planning parameters.
 - 6.5.4. Delivery of Treatment Fraction. Patient is positioned on the treatment couch in the immobilization device with Aquaplast head mask in place. Treatment is delivered on the Tomotherapy unit in the cranial causes direction (Patient travels through the Tomotherapy unit head first). Prior to delivery of therapy, a mega voltage CT (MVCT) scan is performed on the Tomotherapy unit. It is recommended that scanning be over a segment of at least 5 cm, and the initial scans in the head region travel through the entire orbital and oral cavity regions. The MVCT is then

aligned with the treatment planning kilovoltage CT (KVCT) scan using the Tomotherapy system. Therapy then commences treating from the top of the scalp to approximately the sternal notch. At that point in time, a second MVCT is obtained thru the level of the kidneys. Alignment of MVCT to KVCT again occurs and treatment of the rest of the upper torso and abdomen and pelvic regions is accomplished. If deemed appropriate by the M.D., the physicist and/or radiation therapist, a third MVCT scan may be acquired through the pelvic region prior to treating through the pelvis.

The Tomotherapy TMLI inferior border will be clearly identified and marked (tattooed) prior to start of therapy. This marked inferior border of the TMLI field will serve as the "matchline" for matching the AP and PA lower extremity fields used to treat the distal femur and rest of the distal lower extremities. The AP ad PA fields will treat the lower extremities through equally weighted opposed AP/PA fields to the same dose as the TMI fraction and be prescribed to midplane.

6.5.5. The Phase 1 portion of this study will escalate the dose of TMLI through five planned dose levels as described in the section 7.0. For patients receiving two fractions on the same day, there must be a **minimum of six hours between fractions**.

As dose is escalated to the TMI target region, the ribs, liver, spleen, brain and skull will be fixed at 12 Gy (See Appendix XII).

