 - e. Hepatic damage, which can occur in combination with cytoxan or as a single agent and can result in significant hepatic toxicity which, can be fatal.
 - f. Temporary hyperpigmentation of the skin and nail bed changes.
 - g. Grand mal seizures which can be prevented by the prophylactic administration of Dilantin.

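### Section 6.2 gives Dilantin as a flat 900 mg on the first day, with no age or size term, to a study that enrols children from age 6; the later level check cannot correct that first day

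*Combined protocol and SAP*

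**What the plan says.** Section 6.2 (Preparative Chemotherapy Regimen) gives the order as "Begin dilantin 300mg/p.o. t.i.d. times 1 day, then 300mg/p.o./IV daily times 14 days". The text that follows provides for monitoring: "dilantin blood levels will be checked and dose adjusted as needed to meet therapeutic range", with further changes if the clinical picture calls for them.

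The population includes children. Section 5.1.4 states "Patients must be older than 6 years and the upper age limit for this study is 55 years", and section 7.0 defines "Stratum 2: Pediatric patients (6-17 years) with advanced myeloid malignancies or high-risk myelodysplasia". There is no separate pediatric regimen. The other mentions of Dilantin are the busulfan toxicity list in section 3.15 ("Grand mal seizures which can be prevented by the prophylactic administration of Dilantin") and the Study Calendar in Appendix V with its footnote. None of them gives a dose.

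Other drugs in the plan are scaled to body size:

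- Busulfan starts at 22 mg/m², with a ceiling of 32 mg/m².
- Etoposide: "VP-16 30mg/kg based on adjusted ideal body weight will be administered".
- Intrathecal methotrexate (section 6.1.g) is 10 mg/m², "but not more than a total dose of 12mg) will be administered intrathecally".

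The measurements needed for scaling are already taken. Section 6.1.a says "height, weight and body surface area should also be noted".

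**The concern.** A fixed milligram amount gives the smallest patients the most drug for their size. The plan treats Dilantin exposure as something to control, because it adjusts to a therapeutic range. But that control starts only when a level is available, and the largest single-day amount is given before then. For a child at the lower end of the age range, the written order is a multiple of the adult amount per kilogram, and nothing in the readable text tells staff to reduce it.

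What is at stake is the safety of the smaller children in stratum 2, in phase I and among the up to nine additional children in phase II (section 10.2). No endpoint, sample size or escalation rule is said to be affected.

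**Working it through.** **Inputs from the protocol.** First day 300 mg three times; then 300 mg daily (6.2). Pediatric stratum 6-17 years (7.0). The order stands under Day -19 and the level check under Day -15 (6.2). In the Study Calendar the Dilantin level mark appears at Day -13. Both layouts are damaged in the text version.

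**Inputs assumed.** The protocol gives no body weights. Assumed: small child 18-30 kg, larger children 40 and 60 kg, adult 70-80 kg. Body surface is taken as proportional to weight^(2/3).

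**Step 1: first-day amount.** 3 × 300 = 900 mg.

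**Step 2: amount per kilogram.** 900 / weight:

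| Assumed weight | First-day mg/kg |
|---|---|
| 18 kg | 50.0 |
| 30 kg | 30.0 |
| 40 kg | 22.5 |
| 60 kg | 15.0 |
| 70 kg | 12.9 |
| 80 kg | 11.3 |

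**Step 3: child against adult.** The per-kg ratio is adult weight / child weight. The surface-scale ratio is (adult weight / child weight)^(2/3).

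| Child | Per-kg ratio | Surface-scale ratio |
|---|---|---|
| 18-30 kg | 70/30 = 2.33 to 80/18 = 4.44 | 1.76 to 2.70 |
| 40 kg | 70/40 = 1.75 to 80/40 = 2.00 | 1.45 to 1.59 |
| 60 kg | 70/60 = 1.17 to 80/60 = 1.33 | 1.11 to 1.21 |

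**Step 4: can the level check correct the first day?**

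- Day -19 to Day -15 is 4 days. The amount given before that day is 900 + 3 × 300 = 1,800 mg.
- Day -19 to Day -13 is 6 days. The amount given before that day is 900 + 5 × 300 = 2,400 mg.

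On either reading, all of the first 900 mg comes before the first level. The adjustment sentence limits later daily doses only.

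**Step 5: how many children?** This cannot be computed. Section 10.1 expects about 18 patients per stratum if the top dose is well tolerated, which matches 4 × 3 + 6 = 18. With all five levels expanded to six it would be 5 × 6 = 30, and fewer if escalation stops early. The weight mix within stratum 2 is not given.

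**The case against.** The strongest reply has six parts.

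- **No harm is shown.** Any flat dose is larger per kilogram in a smaller person, and the protocol gives no Dilantin threshold against which to judge 900 mg. This stands: the size of the harm is unknown. It does not supply a reason for leaving the starting amount unscaled.
- **The ratios are assumed.** The 4.4 pairs the lightest assumed child with the heaviest assumed adult, and the ratio is close to 1 for large adolescents. This stands, and it confines the concern to the smaller children.
- **Text may be missing.** Two figures next to the order are not shown, and the body-surface equation and busulfan adjustment formula are also lost from this section. A size rule in a figure cannot be excluded, although no text points to one.
- **The SOP manual may cover it.** Section 6.4 sends supportive care to that manual, and Dilantin is given to prevent busulfan seizures. But 6.2 cites the manual for busulfan levels, AUC and stem cell collection, and for Dilantin it writes an amount and cites nothing. If the manual holds a different pediatric dose, the two conflict and the plan does not say which governs.
- **Flat supportive doses occur elsewhere.** The premedication for marrow infusion (diphenhydramine 25 mg, hydrocortisone 50 mg) also has no age term. So the plan's convention is mixed, and consistency alone is a weak argument.
- **Too little also carries risk.** Under-dosing could leave a child unprotected when busulfan starts, and an otherwise unexplained seizure is Grade III CNS toxicity on the modified Bearman Scale, hence a DLT. This is a good reason for clinicians and pharmacy to set the figure. It is not a reason to keep the adult amount.

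**Conclusion.** The concern holds. As written, section 6.2 gives every patient from age 6 upward the same 900 mg on the first day, and its level-based adjustment comes too late to affect that day. Under the stated weight assumptions a small child receives 2.3 to 4.4 times the adult amount per kilogram, or 1.8 to 2.7 times on a surface scale. The excess falls to about 1.1 to 1.3 times at 60 kg.

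The conclusion rests on the readable text and on the SOP manual not overriding the order. The ratios also rest on assumed weights. No overdose is proven, and no effect on DLT or MTD is asserted. Confidence is medium. The change should be made because it is a safety matter with a simple remedy, but this is not a flaw in the statistical design.

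**What to change.** Amend one line of section 6.2. Limit the flat order to stratum 1. For stratum 2, state a size-scaled Dilantin order capped at the adult amount, in the same form as the capped intrathecal methotrexate order in section 6.1.g. The sponsor's pediatric clinicians and pharmacy should set the figure, weighing first-day exposure against seizure protection before busulfan starts. If the SOP manual already holds a pediatric dose, section 6.2 should instead cite it and say that it replaces the flat amount.

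The cost is an amendment of one line. Weight and body surface area are already recorded before admission, so no patient, visit or test is added.
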